#### 4.2 Additional Variables of Interest

Table 3. Description of additional variables

Variable	Description	Variables and Source	Specifications
Age (years)	Age in years	ag_yr  Form: Enrollment form	Range from 1-89
Age group	Age groups	Ag_group  Form: Enrollment form	Participants with Age >89 will be categorized as one group  1=1-89; 2=>89
Sex	Sex of adult or child	sex  Form: Enrollment form	1=Male; 2=Female; 3=Transgender Female; 4=Transgender Male; 5=Gender Variant / Non-Conforming/Not listed/Prefer not to Answer
Race	Race of adult or child	Race_American Indian or Alaska Native; Race_Asian; Race_Black or African American; Race_Native Hawaiian or Other Pacific Islander; Race_White; Race_Other; Race_Other, specify; Race_Unknown or Prefer Not to Answer  Form: Enrollment form	1=Yes; 0=No
Ethnicity	Ethnicity of adult or child	Ethnicity  Form: Enrollment form	1=Hispanic or Latino; 2=Not Hispanic or Latino; 3=Unknown or Prefer Not to Answer
Location	Location of the recruitment	Location  Form:	1=UAMS; 2=AC

		Enrollment form	
Otoscopy findings by ear		Oto_left  Oto_right  Data Collection Form: Audiologist Interpretation for Otscopy	0=Normal; 1= Non-occluding cerumen; 2= Occluding cerumen; 3= Retraction; 4= Effusion; 5= Acute otitis media; 6= Otorrhea; 7= Perforation; 8= Patent tube; 9= Plugged tube; 10= External otitis; 11= Myringitis; 12= Foreign body; 13=Cholesteatoma 14=Tympanosclerosis 15= Could not evaluate; 16= Other

## 5 Analysis Plan

### 5.1 General Considerations

Analysis timeline: The final statistical analysis will be performed after study data is available from 30 participants (60 ears); and the Center for Hearing Health Equity data management team has completed the transfer of an analysis-ready dataset to the study statistician.

Statistical Software: The analysis will be done using SAS (version 9.4) and R (version 4.3.2). A two-sided alpha of 0.05 will be used to determine statistical significance.

### 5.2 Data Summary and Visualization

Descriptive statistics will be presented as n (non-missing sample size); mean (standard deviation) and median (inter quartile range) for continuous variables and as frequency (percentage, based on non-missing sample size) for categorical variables. Descriptive statistics will be presented as overall and by study site (UAMS – adult population vs AC – pediatric population).

### 5.3 Analysis of Primary Endpoints

The primary outcome is the classification of the tympanogram types, which can be categorized into one of the three categories A, B, and C. The classification of tympanogram types from the commercial device (based on audiologist's interpretation) will be considered as reference standard (gold standard). In the subsequent section, the unit of cluster will refer to subjects who contribute to tympanogram types for left and right ears using the prototype as well as the commercial device. The analysis will be done based on a 2-level outcome, namely A (normal) vs B/C (diseased).

Diagnostic accuracy of the prototype device based on audiologist's interpretation: The diagnostic accuracy of the prototype device (based on audiologist's interpretation) will be estimated using sensitivity and specificity. The sensitivity and specificity will be estimated using a binary outcome – A (normal) vs B/C (diseased). To ensure the maximum use of the available data, the estimates of sensitivity and specificity will

be computed at ear-level. Taking into consideration the potential correlation between the two ears, the sensitivity and specificity will be estimated using generalized estimating equation (GEE), with a robust (sandwich) variance estimator and unstructured correlation matrix.

**Secondary analysis of primary endpoints:** The secondary analysis of primary endpoints will constitute additional measures of diagnostic accuracy namely – positive predictive value (PPV), negative predictive value (NPV), positive likelihood ratio (PLR), and negative likelihood ratio (NLR). To obtain estimates of PPV and NPV, the disease prevalence will be set at 0.20 (estimate of disease prevalence may be updated).

**Analysis based on 3-level outcome:** The performance of the prototype device will be presented using a three-by-three confusion matrix. The overall accuracy will be computed from the confusion matrix. We will also compute separate estimates of sensitivity and specificity separately for tympanometric tracing types B and C respectively.

**Agreement between audiologist's and machine learning algorithm's interpretation of the tympanometric tracing types (based on prototype device):** The agreement between audiologist's and machine learning algorithm's interpretation of the tympanometric tracing (based on prototype device) will be tested for statistical significance using Durkalski's adjustment to the McNemar's test statistics for the analysis of clustered matched-pair data (Durkalski et al). Durkalski's method for the analysis of clustered matched-pair data will maximize the use of available data and adjusts for multiple units within a cluster while avoiding any assumptions related to intra-cluster correlation. The Kappa statistic and the corresponding 95% confidence interval will be estimated using cluster-bootstrapped approach (Kang et al). The bootstrapped approach will ensure maximal data usage while also taking into account the potential subject-level clustering. The aforementioned measures of agreement will be based on a 3-level outcome.

**Diagnostic accuracy of the prototype device based on machine learning algorithm's interpretation:** The diagnostic accuracy of the prototype device (based on machine learning algorithm's interpretation) will be estimated using sensitivity and specificity. These estimates will be obtained using the analysis approach described earlier for diagnostic accuracy of prototype device based on audiologist's interpretation. The secondary analysis of diagnostic accuracy as well as the analysis based on 3-level outcome will be done using the approach described earlier for the prototype device based on audiologist's interpretation.

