A minimum of 30 participants will be enrolled. Both ears will be used for each patient enrolled, with enrollment remaining open until 60 ears (40 adult and 20 pediatric ears) are accrued to ensure that there are sufficient number of ears for analysis. It is possible that more than 30 participants will be required to accrue 60 ears if we are unable to obtain a tracing on one or both ears in certain patients (such as due to a draining ear, which inhibits formation of a seal). We anticipate consenting no more than 40 individuals to reach the enrollment goal of 30 participants. With a sample size of 30 participants (60 ears), a null hypothesis where kappa is 0 (no correlation between devices) can be tested against the alternative hypothesis of kappa of 0.3 using a two-sided 0.05 significance level with a power of 0.89.

Title: "Pilot Validation of a Prototype Mobile Health Tympanometer"
PI: [name], MPH
Institution: University of Arkansas for Medical Sciences

Machine Learning Algorithm Analysis

The categorizations of the tympanogram (Type A, B, C) classified by the algorithm will be compared with the audiologists' interpretations. To assess agreement between the audiologist and the algorithm, Kappa analysis and Bowker's test of symmetry will be performed.

Ethical Considerations

This study will be conducted in accordance with all applicable government regulations and UAMS research policies and procedures. This protocol and any amendments will be submitted and approved by the IRB as required.

For recruitment and eligibility determination, a partial HIPAA waiver will be obtained. PHI access under the partial HIPAA waiver will entail using the clinic schedule to screen for potential participants by their age and reason for visit. Reason for visit will be used to determine middle ear status and whether tympanometry is likely to be performed as part of the clinical visit.

For eligible participants and parents/guardian of eligible children, informed consent using IRB-approved consent materials, will be obtained before the participant begins any study procedures and will be performed electronically using a secure REDCap database. All participants for this study will be provided an electronic informed consent form (e-consent) describing this study in language understandable to the study population.

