### 1.3 *Research Objectives and Study Hypotheses*

**Objective 1 (primary):**

To obtain preliminary estimates of the accuracy of the prototype device compared to commercial tympanometer based on audiologist's interpretation (for both devices).

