### 2.2 Power and Sample size

A sample size of 30 participants (60 ears), with an assumed prevalence of 0.20 will yield a half-width of 95% confidence interval ranging from 0.25-0.33 when the sample sensitivity is 0.80; and a half-width of 95% confidence interval ranging from 0.12-0.18 when the sample specificity is 0.80. The range of the half-width of 95% confidence interval reflect the extreme scenario of the intra-class correlation ranging from 0 to 1.

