### **5.5 Subgroup analysis**

The descriptive statistics and the analysis related to primary endpoints will be presented separately for adults and pediatric populations. Owing to small sample size, these results will be considered exploratory.

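### SAP 5.3 gives no interval method that works when every ear in a sensitivity or specificity cell is read correctly, which is a realistic outcome for sensitivity with about 12 diseased ears

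*SAP*

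**What the plan says.** SAP 5.3 takes the commercial device, as read by the audiologist, as the reference. It reduces the outcome to type A against B/C and works at ear level. To allow for correlation between ears, "the sensitivity and specificity will be estimated using generalized estimating equation (GEE), with a robust (sandwich) variance estimator and unstructured correlation matrix". No link function, interval formula or small-sample correction is given, and nothing is said about an all-correct cell or non-convergence.

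For the machine learning reading, "These estimates will be obtained using the analysis approach described earlier for diagnostic accuracy of prototype device". SAP 5.3 also plans "separate estimates of sensitivity and specificity separately for tympanometric tracing types B and C respectively", and SAP 5.5 adds that "the analysis related to primary endpoints will be presented separately for adults and pediatric populations", labelling those results exploratory.

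SAP 2.2 plans precision for 60 ears "with an assumed prevalence of 0.20 will yield a half-width of 95% confidence interval ranging from 0.25-0.33" at a sample sensitivity of 0.80. For a sample specificity of 0.80 it gives 0.12 to 0.18. It says these ranges "reflect the extreme scenario of the intra-class correlation ranging from 0 to 1".

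SAP 1.1 allows justified deviations in general terms. SAP 5.8 lists no sensitivity analysis, and SAP 5.9 deals only with missing data.

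**The concern.** The sandwich variance is built from residuals. A cell without misclassification has none, so the planned method cannot express uncertainty in exactly the case where the prototype performs best. There are two possible symptoms. One is a printed interval of [1,1], which shows false certainty. The other is a fit that stops, after which the replacement interval would be chosen with the data in view.

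Hypotheses 1 and 2B place sensitivity at 80% or more, so the breakdown lies in the region the sponsor hopes to be in. The pilot's estimates are meant to guide device changes and to support a grant application for a larger validation study, so an overstated interval would carry forward.

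**Working it through.** **Inputs.** 60 ears in 30 participants, prevalence 0.20 and ICC 0 to 1 (SAP 2.2); "60 ears (40 adult and 20 pediatric ears) are accrued" (Protocol, Data Analysis); sensitivity of 0.80 or more (SAP 1.3). True sensitivities of 0.90 and 0.95 are assumptions for illustration.

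**1. SAP 2.2's own figures.** Diseased ears: 60 × 0.20 = 12. Normal ears: 48. With ICC 1 and all participants bilateral, the effective numbers halve to 6 and 24. Half-widths at a proportion of 0.80:

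| Effective n | Clopper-Pearson | Wald | SAP 2.2 |
|---|---|---|---|
| 12 (sensitivity, ICC 0) | 0.244 | 0.226 | 0.25 |
| 6 (sensitivity, ICC 1) | 0.331 | 0.320 | 0.33 |
| 48 (specificity, ICC 0) | 0.121 | 0.113 | 0.12 |
| 24 (specificity, ICC 1) | 0.173 | 0.160 | 0.18 |

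The exact interval reproduces all four figures to within 0.01. The precision planning therefore matches an exact-type interval, which SAP 5.3 does not carry forward.

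**2. Why the method breaks.** Under working independence, Var(p̂) = Σᵢ(Σⱼ(yᵢⱼ − p̂))² / n², with i the participant and j the ear. If every y is 1, then p̂ = 1, every residual is 0 and the variance is 0. Another working correlation only reweights the same zero residuals.

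**3. Fits in statsmodels, 12/12 correct.**
- Logit link, unstructured correlation, with 4 bilateral and 4 single-ear participants or with 6 bilateral: intercept 24.57, interval [1.000, 1.000].
- 1 bilateral and 10 single-ear: [1,1] under independence; the unstructured fit stops.
- Identity and log links, unstructured: the fit fails.
- Joint 60-ear model: logit unstructured stops with infinite or undefined values; logit independence gives [1.000, 1.000]; identity unstructured gives [0.99999, 1.00000].
- One misread ear restores a usable interval: 11/12 in 6 bilateral participants gives [0.610, 0.987] (logit, unstructured).

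**4. How likely it is.** With independent ears, P(all correct) = sⁿ.

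| Diseased ears | s = 0.80 | s = 0.90 | s = 0.95 |
|---|---|---|---|
| 12 (SAP 2.2) | 0.07 | 0.28 | 0.54 |
| 24 (more pathology recruited) | 0.005 | 0.08 | 0.29 |
| 8 (adults, 40 × 0.20) | 0.17 | 0.43 | 0.66 |
| 4 (children, 20 × 0.20) | 0.41 | 0.66 | 0.81 |

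For 6 bilateral pairs with between-ear correlation r, P = (s² + r·s(1−s))⁶. With r = 0.5 this gives 0.14 / 0.39 / 0.63, and with r = 1 it gives 0.26 / 0.53 / 0.74. The independent-ear figures are therefore the low end of SAP 2.2's ICC range. Specificity is much less exposed: with 48 independent ears, 0.80⁴⁸ is about 0.00002, 0.90⁴⁸ = 0.006 and 0.95⁴⁸ = 0.09.

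**5. What an honest interval looks like.** For n/n the exact 95% lower limit is 0.025^(1/n). With n = 12 it is 0.735, and with n = 6 it is 0.541.

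**The case against.** SAP 1.1 foresees deviations and requires them to be justified. A [1,1] interval or a separation warning would be hard to miss, and the planned confusion matrix would show the counts. The study is a pilot, and Objective 1 is "To obtain preliminary estimates of the accuracy of the prototype device compared to commercial tympanometer". Patients are selected for middle ear pathology (Protocol, Study Design and Procedures), so the diseased count may well exceed 12. The fits were run in neither SAS nor R. SAP 5.3 does not spell out an interval formula, so taking the interval from the sandwich variance is an inference, and the table shells are in a separate document that was not available.

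Most of this limits the size of the problem without removing it. More diseased ears do lower the probability, and other software may show a different symptom, but zero residuals give no variance information in any package. A general permission to deviate does not say which interval will be used. By contrast, SAP 5.4 names data transformation as a possible alternative if the Bland-Altman assumptions fail.

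Three stronger readings are tempting and are not supported. A reader might infer that the GEE analysis is unworkable at this sample size; one misread ear is enough to give a usable interval. A reader might infer that the trial would formally declare 80% sensitivity on a [1,1] interval; the plan seeks preliminary estimates and has no test against 0.80, so the risk is one of presentation. A reader might take 0.07 / 0.28 / 0.54 as forecasts; they depend on 12 diseased ears, independent ears and assumed true sensitivities.

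**Conclusion.** The gap is real and should be closed before the data are seen. The only method named for the primary sensitivity and specificity gives no valid interval when a cell has no misread ear, and the SAP names no replacement. On SAP 2.2's planning figures with independent ears, the chance of this for sensitivity is 0.07 / 0.28 / 0.54 at true sensitivity 0.80 / 0.90 / 0.95. Up to full correlation within six pairs it rises to 0.26 / 0.53 / 0.74; with 24 independent diseased ears it falls to 0.005 / 0.08 / 0.29. The same gap affects Objective 2B. It is wider in the smaller type B, type C and exploratory subgroup cells.

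**What to change.** In SAP 5.3, keep the GEE as planned. For every sensitivity and specificity cell (Objectives 1 and 2B, type-specific and subgroup estimates), also report the ear-level proportion p̂ with Clopper-Pearson limits at both ends of SAP 2.2's ICC range:

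- ICC 0: n = ears in the cell.
- ICC 1: n = participants contributing an ear to the cell, with the count scaled to x = n·p̂.

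The lower limit is the 0.025 quantile of Beta(x, n−x+1), and the upper limit is the 0.975 quantile of Beta(x+1, n−x). They are set to 0 when x = 0 and to 1 when x = n. Where all or no ears are correct, or the GEE does not converge, this bracket stands in place of the GEE interval.

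Showing the bracket in every cell matters. If exact limits appeared only in all-correct cells, six pairs at 12/12 would have an ICC 1 lower limit of 0.541, against 0.610 from the GEE at 11/12, so the better result would look worse. On one scale this cannot happen:

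| Result | Lower limit, ICC 1 | Lower limit, ICC 0 |
|---|---|---|
| 6 pairs, 12/12 | 0.541 | 0.735 |
| 6 pairs, 11/12 | 0.442 | 0.615 |
| 15 pairs, 30/30 | 0.782 | 0.884 |
| 15 pairs, 29/30 | 0.728 | 0.828 |

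Do not attach a pass criterion at 0.80, and do not switch between GEE and exact limits to decide whether 80% has been shown. The cost is a short addition to SAP 5.3 and a few lines of code, with no extra participants. The drawback is that the ICC 1 limits are conservative and wider.

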**Objective 2A:**

To obtain preliminary estimates of the agreement between audiologist's interpretation of the prototype device and machine learning algorithm's interpretation of the prototype device.

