**Hypothesis 2A:**

The categorical classifications of tympanogram types based on audiologist's interpretation of the prototype device versus machine learning algorithm's interpretation of the prototype device are not significantly different.

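### Hypothesis 2A rests audiologist-versus-algorithm agreement on a non-significant clustered McNemar test, which checks calling balance, and no three-category form of that test is named

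*SAP*

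**What the plan says.** Objective 2 is labelled primary (SAP 1.3). Its part 2A begins "To obtain preliminary estimates of the agreement between" and names the audiologist and the ML algorithm, both reading the prototype. Hypothesis 2A is that the two sets of classifications, ending with the algorithm's "interpretation of the prototype device are not significantly different". No margin, minimum kappa or other criterion is attached.

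SAP 5.3 says this agreement will be tested for significance using Durkalski's adjustment to McNemar's "test statistics for the analysis of clustered matched-pair data", chosen because it "adjusts for multiple units within a cluster while avoiding any assumptions related to intra-cluster correlation". SAP 5.1 sets a two-sided alpha of 0.05. The same paragraph of 5.3 adds: "The Kappa statistic and the corresponding 95% confidence interval will be estimated using cluster-bootstrapped approach". It closes: "The aforementioned measures of agreement will be based on a 3-level outcome".

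Two other statements in 5.3 bear on the outcome level. The opening gives a general rule, "The analysis will be done based on a 2-level outcome, namely A (normal) vs B/C (diseased"). A later paragraph goes to three levels for the device comparison: "The performance of the prototype device will be presented using a three-by-three confusion matrix".

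The Protocol (Machine Learning Algorithm Analysis) plans kappa and Bowker's test of symmetry for the audiologist-algorithm comparison.

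**The concern.** The objective asks how well two readers agree. The hypothesis is the null of a test that asks whether they call categories at the same rate. Ears on which the readers agree do not enter a McNemar-type statistic, and errors in opposite directions cancel. If the plan is followed as written, a non-significant p-value would count as support for 2A even when the algorithm's calls bear no relation to the audiologist's. Kappa would show this, but nothing in the SAP ties 2A to kappa. A report could therefore show a p-value and a kappa pointing opposite ways, with no rule for which one settles the hypothesis. SAP 2.1 says the pilot data will inform whether the algorithm needs more refinement, so a misread 2A has some consequence.

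The second problem lies inside the agreement paragraph. It calls for three levels straight after describing both the test and kappa, but the named test is for paired binary data. To run it, the analyst must either collapse to A versus B/C or use a clustered multi-category extension. The SAP names neither.

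**Working it through.** **Inputs.** 30 participants, 60 ears and prevalence 0.20 (SAP 2.2); two-sided alpha 0.05 (SAP 5.1). Assumed here: the algorithm's call rates and error patterns, an even 6/6 split of the 12 abnormal ears into B and C, and between-ear correlation anywhere from 0 to 1 (the range SAP 2.2 uses for its own calculation).

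**The plan's own figure.** No power or precision is given for 2A. The only agreement figure is the Protocol's power of 0.89 for kappa 0.3 against 0, stated for device versus device. Power = Φ[(0.3 − 1.96·SE0)/SE1].
- Three equally likely categories, 60 independent ears: chance agreement is 1/3, SE0² = (1/3 + 1/9 − 2/9)/(60 × 4/9) = 0.00833, so SE0 = 0.0913. With SE1 = 0.0966, power = 0.895, which matches.
- Two categories: SE0 = 1/√60 = 0.129 and power is only 0.62-0.65.

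The Protocol's figure therefore fits a three-level outcome.

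**Test statistic.** For participant k with n_k ears, let b_k be the ears the audiologist calls B/C and the algorithm calls A, and c_k the reverse. With d_k = (b_k − c_k)/n_k, the statistic is (Σ d_k)² / Σ d_k², referred to chi-square on 1 df.

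**1. Balanced but unrelated calls (A versus B/C).** Take 38 ears both A, 2 both B/C, and 10 discordant each way.
- Observed agreement is 40/60 = 0.667. Chance agreement is (48² + 12²)/60² = 0.68. Kappa = (0.667 − 0.68)/0.32 = −0.04.
- Unadjusted McNemar: (10 − 10)²/20 = 0, p = 1.00.

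**2. How often a kappa-0 algorithm is non-significant.** Simulation of the Durkalski statistic with independent readers and latent-normal correlation between ears. The audiologist calls 20% B/C.

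| Algorithm's B/C rate | Non-significant, correlation 0 to 1 |
|---|---|
| 20% | 95-96% |
| 30% | 76-87% |
| 40% | 34-63% |
| 50% | 7-33% |

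**3. High agreement with one-way errors.** The algorithm calls 4 Type A ears B and is otherwise right.
- Observed agreement is 56/60 = 0.933. Chance agreement is (48×44 + 6×10 + 6×6)/3600 = 0.613. Three-level kappa = 0.320/0.387 = 0.83.
- Errors in 4 participants: each d_k = 1/2 in size, statistic = 2²/(4 × 0.25) = 4.00, p = 0.046.
- In 3 participants: 4/(1 + 0.25 + 0.25) = 2.67, p = 0.10.
- In 2 participants: 4/(1 + 1) = 2.00, p = 0.16.

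Kappa is the same in all three layouts, yet the p-value crosses 0.05 according to which participants the errors fall in. If 8% of Type A ears are called B (mean kappa about 0.83), the test is significant in about 49%, 35% and 12% of trials at correlation 0, 0.5 and 1.

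**4. The level changes the answer.** Swap B and C in all 12 abnormal ears.
- Three-level: observed 48/60 = 0.80, chance (48² + 6² + 6²)/3600 = 0.66, kappa = 0.14/0.34 = 0.41.
- A versus B/C: no discordant ears, so kappa is 1.00 and the clustered test has nothing to detect.

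**The case against.** - **Kappa is already planned.** This stands. The three-level kappa with its cluster-bootstrap interval delivers Objective 2A. A reader might infer that the plan has no measure of agreement; it has one. What is missing is a link from Hypothesis 2A to it.
- **The sections do not truly conflict on level.** A reader might infer a contradiction between the two-level opening of 5.3 and the three-level close of the agreement paragraph. The opening is better read as a default: 5.3 itself departs from it elsewhere, and the specific sentence matches Objective 2's types A, B, C and the Protocol. The default adds ambiguity, but the core defect is a paired-binary test attached to a three-level outcome.
- **A significant result with one-way errors is not a false alarm.** Correct: it properly signals over-calling. It misleads only if read as poor agreement. Hypothesis 2A does not use the word agreement; the mismatch is between the hypothesis and its objective.
- **The 95-96% is an extreme case.** It needs zero ear-level association and equal call rates. Nothing in the documents suggests such an algorithm, and the table shows how fast the figure falls.
- **Little hangs on the p-value.** No stopping or go/no-go rule uses it, the study is a pilot seeking preliminary estimates, and Hypothesis 2B's 80% target would expose a poor algorithm. This limits the harm but does not settle what a hypothesis under a primary objective means.
- **Dropping Bowker's test might look like a weakening.** It is not. In simulation with equal 20% B/C rates and kappa 0, unadjusted Bowker rejects in 2.7% of trials at between-ear correlation 0 and 19.7% at correlation 1, while the Durkalski test stays near 5%. Bowker is also a symmetry test, so going back to it would not cure the reading of non-significance.

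**Conclusion.** The point holds as a defect of interpretation and specification, worth fixing before analysis. Non-significance of the clustered McNemar test cannot support audiologist-algorithm agreement: a kappa-0 algorithm would pass in 95-96% of trials at equal call rates, falling to 7-33% if it called 50% of ears B/C. The test as named also cannot be run on three levels without a choice the SAP does not make, and that choice can move kappa from 0.41 to 1.00.

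The documents do not support the stronger inferences that agreement goes unestimated or that the clustered test is a poor choice for checking calling bias. The qualitative conclusion follows from the form of the statistic. The percentages rest on the SAP's 20% prevalence, two evaluable ears in every participant, and assumed call rates, error rates and between-ear correlation.

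**What to change.** 1. Reword Hypothesis 2A as an estimation statement, reported by the planned three-level kappa and its cluster-bootstrap 95% interval. State that the McNemar-type p-value does not decide 2A. If the team wants a yes/no conclusion, it must prespecify a lower limit for the kappa interval; the value is theirs to choose.
2. State the level for each 2A analysis: three-level for kappa; for the Durkalski test, either A versus B/C or a named clustered multi-category version. In both cases label it a check for systematic over- or under-calling by the algorithm.
3. Show the three-by-three audiologist-by-algorithm table beside these results. The SAP text specifies such a matrix only for comparisons with the commercial reference. The table shells are in a separate document not available here, so this table may already be planned.
4. Housekeeping: add a sentence saying that the clustered test replaces the Protocol's unadjusted Bowker test, and why.

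The cost is SAP wording and at most one table, with no new data. The downside is that an agreement claim becomes harder to make. If the two-level check is chosen it cannot see confusion between B and C, so the three-level kappa and table must sit beside it.
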